5.1 DEFINITIONS

Adverse Events

An Adverse Event (AE) is any untoward medical occurrence in a participant administered at least one dose of study medication; the event does not necessarily have a causal relationship with that treatment or usage. All adverse events (see exception for cancer-related chemotherapy below) will be reported

An adverse event can therefore be:

- All suspected adverse medication reactions.
- All reactions from medication abuse, withdrawal, sensitivity, or toxicity.
- Apparently unrelated illnesses, including the worsening of a pre-existing illness (definition below).
- Injury or accidents.
 - Note that if a medical condition is known to have caused the injury or accident (e.g., a fall secondary to dizziness), the medical condition (dizziness) and the accident (fall) will be reported as two separate AEs.
- Abnormalities in physiological testing or physical examination (findings that require clinical intervention or further investigation beyond ordering a repeat [confirmatory] test).

- Laboratory abnormalities that require clinical intervention or further investigation (beyond ordering a repeat [confirmatory] test) unless they are associated with an already reported clinical event. Laboratory abnormalities associated with a clinical event (e.g., elevated liver enzymes in a subject with jaundice) will be described as a separate AE.

Serious Adverse Events

Serious Adverse Event (SAE)

- An event that results in death
- An event that places the participant at immediate risk of death (a life-threatening event). This does not include an event that, had it occurred in a more severe form, might have caused death.
- Requires participant hospitalization or prolongation of existing hospitalization. For this study, the following exceptions apply to the index hospitalization:
 - Hospitalization for routine administration of chemotherapy/radiation therapy or monitoring of chemotherapy/radiation therapy side effects will not be recorded as a serious adverse event.
- Results in persistent or significant disability/incapacity.
- Is a congenital anomaly/ birth defect
- Other medically important events that, in the opinion of the Site Investigator, may jeopardize the participant or may require intervention to prevent one of the other outcomes listed in the definition above.

Some conditions may not be immediately life threatening or require hospitalization. Should the investigator feel that the event may jeopardize the participant or may require intervention to prevent more serious outcomes, then it should be treated as serious.

Pre-Existing Conditions

In this trial, a pre-existing condition (i.e., a disorder present before the adverse event reporting period started) should not be reported as an adverse event unless the condition worsens during the adverse event reporting period.

Procedures

Diagnostic and therapeutic non-invasive and invasive procedures, such as surgery, should not be reported as adverse events. However, the medical condition for which the procedure was performed should be reported if it meets the definition of an adverse event.

Laboratory Test Abnormalities

Laboratory test value abnormalities will be reported as an AE if they satisfy one or more of the following conditions for clinical significance:

1. Accompanied by clinical symptoms
2. Leading to a change in study medication (e.g. Dose modification, interruption or permanent discontinuation)
3. Requiring a change in concomitant therapy (e.g. Addition of, interruption of, discontinuation of, or any other change in a concomitant medication, therapy or treatment).

Please note: any laboratory result abnormality fulfilling the criteria for a serious adverse event (SAE) should be reported as such, in addition to being recorded as an adverse event in the CRF.

GRADING OF ADVERSE EVENTS

All adverse events will be graded by the Investigator using the scale below.

1=Mild	Discomfort noticed but no disruption of normal daily activity
2=Moderate	Discomfort sufficient to reduce or affect daily activity
3=Severe	Inability to work or perform normal daily activity

CAUSALITY

Relationship of all adverse events and serious adverse events to the study interventions (causality) should be assessed by the investigator as follows:

- **Unrelated:** There is not a reasonable possibility that the adverse event may have been caused by the study drug.
- **Possibly related:** The adverse event may have been caused by the study drug, however there is insufficient information to determine the likelihood of this possibility.
- **Related:** There is a reasonable possibility that the adverse event may have been caused by the study drug.

EXPECTEDNESS

Adverse events and serious adverse events will also be assessed according to the following categories:

- **Expected (anticipated):** the event is identified in nature, severity, or frequency in the investigator brochure, product monograph or in the protocol.
- **Unexpected (unanticipated):** the event is not identified in nature, severity, or frequency in the investigator brochure, the product monograph or in the protocol.

CANCER RELATED AES

For this study, adverse events that are possibly related or related to cancer and its treatment will not be recorded as an adverse event. However, if the cancer related event meets the criteria of a SAE, the event will be recorded and reported accordingly regardless of the causality. These include but are not limited to:

- Nausea
- Vomiting
- Changes in bowel function – including constipation, diarrhea, bloating or flatulence
- Abnormal white blood cell count
- Urinary symptoms
- Appetite changes
- Fatigue or lethargy
- Hair loss
- Mouth or throat changes
- Weight loss
- Confusion or altered level of consciousness
- Progression of cancer

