5.2 RECORDING, REPORTING AND FOLLOW -UP OF ADVERSE EVENTS

Adverse Events Recording

Adverse events will be recorded on the CRF.

The investigator and delegates will record all directly observed adverse events and all adverse events spontaneously reported by the participant. In addition, each participant will be questioned about adverse events at each visit.

Adverse Events Reporting

The QI or delegate will be responsible for reporting the AEs to the OHSNREB, and the Data and Safety Monitoring Board (DSMB) as follows:

- Adverse events will be reported to the OHSNREB as per their guidelines
- Adverse events will be summarized in a table and provided to the Data and Safety Monitoring Board (DSMB) before DSMB meetings.

Serious Adverse Events Reporting

SAEs require prompt or immediate reporting to the QI or delegate. The QI is ultimately responsible for reporting the SAEs to Health Canada, the OHSNREB, the Data and Safety Monitoring Board and Bayer.

Reporting to Health Canada

Serious adverse events that are both unexpected and related or possibly related are subject to expedited reporting to Health Canada. SAEs that are expected or that are unrelated to the study drug are not reportable.

All sites will report to the coordinating centre and the sponsor of the trial will be responsible for reporting the SAE to Health Canada

Report must be filed in the cases:

- I. where the SAE is neither fatal nor life-threatening; within 15 days after becoming aware of the information
- II. where it is fatal or life-threatening, immediately where possible and, in any event, within 7 days after becoming aware of the information

Within 8 days after having informed Health Canada of the SAE, the Qualified investigator will submit as complete as possible, a report which includes an assessment of the importance and implication of any findings.

Each SAE which is subject to expedited reporting should be reported individually using the TRIM-Line form (see Appendix).

Any updated follow up information that becomes available regarding the SAE should be reported in a follow up report.

Reporting to the OHSNREB

All SAEs will be reported to the OHSNREB as per their guidelines.

Reporting to the Data Safety Monitoring Board (DSMB)

SAEs that are related or possibly related and unexpected will be reported immediately to the Chair of the DSMB.

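### Section 5.1 both exempts and requires a separate adverse event for a laboratory abnormality linked to a clinical event, so non-serious AE counts can differ between sites

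*Protocol*

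**What the plan says.** Three statements in Protocol section 5.1 bear on when a laboratory result is an adverse event.

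- **Adverse Events, last bullet, first sentence.** The trigger is "Laboratory abnormalities that require clinical intervention or further investigation (beyond ordering a repeat [confirmatory] test"), and the exception, running into the start of the next sentence, reads "unless they are associated with an already reported clinical event. Laboratory abnormalities associated with a clinical event".
- **Same bullet, next sentence in full.** "Laboratory abnormalities associated with a clinical event (e.g., elevated liver enzymes in a subject with jaundice) will be described as a separate AE".
- **Laboratory Test Abnormalities, later in 5.1.** "Laboratory test value abnormalities will be reported as an AE if they satisfy one or more of the following conditions for clinical significance". Three conditions follow: symptoms ("Accompanied by clinical symptoms"), a change in study medication, or a change in concomitant therapy. Further investigation is not on this list.

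No sentence ranks these statements. Section 5 makes the clinical investigators, and ultimately the Qualified Investigator, responsible for identifying AEs. Section 5.2 then sends the counts to the monitoring board: "Adverse events will be summarized in a table and provided to the Data and Safety Monitoring Board (DSMB) before DSMB meetings". Under Stopping Rules, section 5.2 says that the study has no formally defined rules and leaves the decision to stop the experimental therapy to the DSMB's discretion.

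**The concern.** The two sentences of the bullet point in opposite directions for the same result. If the clinical event is already on the form, one sentence says not to add the laboratory finding and the other says to add it. A coordinator cannot follow both, and the protocol is the document a coordinator would consult.

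What is at stake is the meaning of the non-serious AE count. The pilot runs at three centres, so the text allows one centre to enter a linked result separately and another to fold it into the event. The DSMB has no numerical boundary and judges from the data put before it, so the unit of counting should be the same for every participant. An analysis plan cannot fully repair this, because the choice is made when the site fills in the form.

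**Working it through.** The protocol gives no figure on this point, so the check sets the rules side by side over typical cases. A is the bullet's first sentence with its exception, B is the bullet's second sentence, and C is the list under Laboratory Test Abnormalities.

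| Case | A | B | C | Result |
|---|---|---|---|---|
| 1. Raised liver enzymes, jaundice already reported, further investigation needed | no AE | separate AE | AE (symptoms) | conflict |
| 2. Isolated ALT rise leading to imaging, no change in any treatment | AE | not applicable | not listed | conflict only if C is exhaustive |
| 3. Result linked to a reported, symptomatic event, no intervention or further investigation needed | no AE | separate AE | AE (symptoms) | conflict |
| 4. Isolated result leading to study drug being held | AE | not applicable | AE | agree |
| 5. Isolated result leading to a change in concomitant therapy | AE | not applicable | AE | agree |

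The table rests on three readings: jaundice counts as a clinical symptom (case 1), B is not limited to results that meet A's trigger (case 3), and holding study drug counts as an intervention (case 4).

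The rules part in 3 of the 5 cases. In two of these (1 and 3) the result is linked to a reported event and the instructions are opposed. In the third (2) the list says when a result is reported but does not say that nothing else is, so A's further-investigation trigger can stand beside it.

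Case 1 is the protocol's own example and does not depend on C.

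Effect on the count, for one clinical event with one linked result:

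- under A: 1 AE (the clinical event);
- under B: 1 + 1 = 2 AEs.

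The documents give no expected number of such events, so a total cannot be derived.

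The limits on how often this can arise also come from the protocol:

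- Laboratory tests are marked only at baseline in the schedule of events, and the Day 30 contact is by telephone (4.14). Later results reach the AE form through participant report or chart review (section 5).
- Non-serious events related or possibly related to cancer or its treatment are not recorded (5.1, Cancer Related AEs).
- A laboratory result that meets the SAE criteria is reported as an SAE and also recorded as an AE (5.1), whichever rule is used for the rest.

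**The case against.** The strongest reply is that this is a slip of the pen: a dropped negative in the second sentence would bring it into line with the first, and experienced staff would read it so. That is plausible, but the text does not settle it. The same list tells sites to report a fall and the dizziness that caused it as two separate AEs, a neighbouring convention that favours splitting. Nor does the word *already* in the exception rescue the bullet. The second sentence carries no such limit, and a separate AE presupposes that the clinical event has one of its own.

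A second reply is that the DSMB is not confined to raw counts. It receives SAE tables and immediate reports of unexpected SAEs that are related or possibly related, and its statistician has data from the central database. This stands as a limit on the harm. It does not remove the problem, since AEs reach the coordinating centre as each site enters them in the eCRF.

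A reader might also infer more than the documents support:

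- *That there are three mutually contradictory rules.* On further investigation, the later list differs from the bullet; it contradicts it only if read as exhaustive.
- *That platelet or haemoglobin counts are distorted.* An isolated platelet result that leads to a hold is an AE under both rules (case 4). Haemoglobin is not named in the protocol, and platelets and ALT appear as eligibility limits (platelets also as a hold criterion), not as named risks of the drug.
- *That the problem carries into the full trial through pooling.* Section 8.1.4 lists VTE, ATE, three bleeding categories, medication intolerance or reaction, and mortality, compared as proportions. It lists no laboratory-AE count, and a bleed is analysed as a bleed whether or not a laboratory result is entered beside it.
- *That sites do count differently.* The text permits it; nothing shows that it has happened.

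**Conclusion.** The contradiction within the bullet is real and is reinforced by the symptom condition in the later list. The protocol as written lets the same non-serious, linked laboratory result be recorded as one AE or two in the table that goes to the DSMB.

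It is a minor point. It is confined to non-serious laboratory AEs not attributed to cancer or its treatment, and few are likely, because laboratory tests are scheduled only at baseline. The recruitment outcome, the sample size, SAE reporting, and the planned VTE and bleeding analyses do not depend on it. The conclusion rests on the wording of section 5.1 alone and on the absence of any statement of precedence. It makes no assumption about how sites have behaved. The missing further-investigation trigger is best treated as a difference to tidy up at the same time.

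**What to change.** Reconcile the two parts of section 5.1 into one recording rule, stated once and cross-referenced from the other place. The rule should do two things.

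1. Say whether a laboratory abnormality linked to a reported clinical event is recorded within that event or as a separate AE. For example, delete the separate-AE sentence, or restore the negative if one was dropped. If the sponsor prefers to split, in keeping with the fall-and-dizziness note, remove the exception instead.
2. Give a single list of triggers for unlinked abnormalities: clinical symptoms, a change in study medication, a change in concomitant therapy, clinical intervention, and further investigation beyond a repeat test.

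The cost is a wording amendment and a line in the CRF instructions, with no extra tests. If linked results are folded into the event, they no longer appear as separate AE lines, so the event description has to carry them.

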5.2 RECORDING, REPORTING AND FOLLOW -UP OF ADVERSE EVENTS

Adverse Events Recording

Adverse events will be recorded on the CRF.

The investigator and delegates will record all directly observed adverse events and all adverse events spontaneously reported by the participant. In addition, each participant will be questioned about adverse events at each visit.

Adverse Events Reporting

The QI or delegate will be responsible for reporting the AEs to the OHSNREB, and the Data and Safety Monitoring Board (DSMB) as follows:

- Adverse events will be reported to the OHSNREB as per their guidelines
- Adverse events will be summarized in a table and provided to the Data and Safety Monitoring Board (DSMB) before DSMB meetings.

Serious Adverse Events Reporting

SAEs require prompt or immediate reporting to the QI or delegate. The QI is ultimately responsible for reporting the SAEs to Health Canada, the OHSNREB, the Data and Safety Monitoring Board and Bayer.

Reporting to Health Canada

Serious adverse events that are both unexpected and related or possibly related are subject to expedited reporting to Health Canada. SAEs that are expected or that are unrelated to the study drug are not reportable.

All sites will report to the coordinating centre and the sponsor of the trial will be responsible for reporting the SAE to Health Canada

Report must be filed in the cases:

- I. where the SAE is neither fatal nor life-threatening; within 15 days after becoming aware of the information
- II. where it is fatal or life-threatening, immediately where possible and, in any event, within 7 days after becoming aware of the information

Within 8 days after having informed Health Canada of the SAE, the Qualified investigator will submit as complete as possible, a report which includes an assessment of the importance and implication of any findings.

Each SAE which is subject to expedited reporting should be reported individually using the TRIM-Line form (see Appendix).

Any updated follow up information that becomes available regarding the SAE should be reported in a follow up report.

Reporting to the OHSNREB

All SAEs will be reported to the OHSNREB as per their guidelines.

Reporting to the Data Safety Monitoring Board (DSMB)

SAEs that are related or possibly related and unexpected will be reported immediately to the Chair of the DSMB.

All SAEs, whether related to the study interventions or not will be summarized in a table, and provided to the DSMB before each scheduled DSMB meeting.

Reporting Procedures for Adverse Events by all sites			
Gravity	Reporting Time	Report to	Type of Report
Serious (fatal or life-threatening) if unexpected and related/possibly related)	Immediately	1) Local REB 2) PI (Ottawa/coordinating Centre) by fax and email	Initial Report
	Within 7 days post initial report then every 15 days if ongoing until end of event		Follow-up/Final Report
Serious (non-fatal or non-life-threatening) whether expected/unexpected or related/unrelated)	Within 24 hours Within 15 days post initial report then every 15 days if ongoing until end of event	1) Local REB 2) PI (Ottawa/coordinating Centre) by fax and email	Initial Report Follow-up/Final Report
AEs	7days	1) PI (Ottawa/coordinating Centre) by entering in	Adverse Event Form in eCRFs

NOTE: In the rare event that the investigator does not become aware of the occurrence of a SAE immediately (e.g., if a trial participant initially seeks treatment elsewhere), the investigator is to report the event within 24 hours after learning of it and document his/her first awareness of the AE.

Adverse Events Follow-Up

Follow-up of adverse events considered related or possibly related to study drugs should continue until they have returned to baseline status or stabilized, or the causal relationship has been changed from related to unrelated to study drug.

Stopping Rules

The study has no formally defined stopping rules. Data will be monitored as they accumulate, and the use of the experimental therapy will cease if there is clear evidence of rivaroxaban-related adverse events or of a lack of efficacy. This decision will be at the discretion of the DSMB

5.3 MANAGEMENT OF MAJOR BLEEDING

All participants with major bleeding (ISTH definition) will have study drug held until judged safe to resume by the investigator.

Treatment Arm

In the event of hemorrhagic complications in a participant receiving rivaroxaban, treatment should be temporarily discontinued, and the source of bleeding investigated. Rivaroxaban has a half-life of approximately 5 to 13 hours. Consideration should be given to the resumption of anticoagulant therapy at the discretion of the treating physicians, when clinically appropriate to adequately control risk of underlying thrombosis.

Management of bleeding should be individualized according to the severity and location of the bleeding. Appropriate symptomatic treatment should be used as needed, such as mechanical compression (eg, for severe epistaxis), surgical hemostasis with bleeding control procedures, fluid replacement and hemodynamic support, blood products (packed red cells or fresh frozen plasma, depending on associated anemia or coagulopathy) or platelets.

If bleeding cannot be controlled by the above measures, consider administration of prothrombin complex concentrate (PCC). However, there is currently only very limited experience with the use of these products in individuals receiving rivaroxaban. A specific antidote for rivaroxaban is not available.

Non-treatment arm

Management of bleeding will be at the discretion of the attending physician.

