4.2 TRIAL DESIGN

TRIM-Line is an open-label, randomized controlled feasibility pilot trial comparing rivaroxaban 10mg po daily vs standard of care (no treatment) in patients with active cancer and indwelling CVC. This will involve 3 centres, Ottawa as the coordinating centre, Halifax and Edmonton.

Cancer patients with insertion of CVC will be eligible.

While the primary outcome is feasibility based clinical data will be collected using the same methodology as the proposed full-sized trial. Should there be no major changes to the trial design based on the findings of this pilot study's feasibility data that would render the collected data inappropriate for inclusion, the clinical data collected during this trial will be included in the primary and secondary analysis for the full trial.

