4.3 TRIAL INTERVENTION

Eligible and consenting patients will receive rivaroxaban 10 mg tablets to be taken once daily, starting within 72 hours of CVC placement. Randomization will occur in a 1:1 ratio via a central web-based randomization system.

The study drug will be continued until the CVC is removed, until one of the study outcomes is achieved, or until the end of the follow-up (90 Days +/- 3 days). Study medication will be held if the platelet count is $50 \times 10^9/L$ or less, the CrCl falls below 30mL/min, the patient experiences bleeding or the patient is required for treatment of cancer to start on a medication or chemotherapy which has a major interaction with rivaroxaban. All patients will be followed for 90 days (+/-3 days), unless they die or withdraw permission for follow up. At the end of the trial, VTE prophylaxis will be left to the discretion of the local investigator.

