4.5 WHAT ARE THE MEASURED OUTCOMES FOR THE PILOT STUDY?

The primary feasibility outcome for the pilot study is the number of participants recruited per centre per month. We will obtain baseline details of the patient's type, location and treatment of cancer, and medications. Secondary feasibility outcomes of the pilot study will include, consent rates, loss to follow up, adherence to therapy defining 80% or greater medication taken as having good adherence to study drug, proportion of screened patients who meet eligibility criteria. We will document reasons for non-consent in order to assist recruitment for the larger multicentre trial.

For the full multicentre trial the outcomes would be as follows: primary outcome of symptomatic, radiographically confirmed VTE. Secondary outcomes include major and CRNMB, CVC life span, premature CVC removal, CVC lumen occlusion, CVC associated infection and death.

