4.15 WITHDRAWAL OF SUBJECTS

A subject has completed the study once all follow-up procedures have been completed. Study drug is discontinued, and appropriate clinical management is initiated in the case of the following outcome events (as defined in section 4.5).

For the subjects who reach a study endpoint, subsequent treatment will be left up to the discretion of the treating physician and documented.

If the subject is prematurely discontinued from participation in the study, the study personnel will make every effort to obtain, and record, information about the reasons for discontinuation and any adverse events and if possible perform all safety assessments.

A subject may voluntarily withdraw participation in this study at any time, including for future data collection. If the subject does not return for a scheduled visit, every effort will be made to contact the subject. In any circumstance, every effort will be made to document the reason for withdrawal and when possible, all safety assessments will be done.

All data will be reported for any subject randomized and not completing the study. Subjects withdrawn as a result of an adverse event thought to be related to the study drug will not be replaced. All safety data collected from all subjects during the study will be analyzed.

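### For major bleeding and CRNMB, sections 4.3 and 4.15 end study drug while 4.3 and 5.3 only hold it, and no rule says which governs

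*Protocol*

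**What the plan says.** Four sections of the protocol bear on what happens to study drug after a bleed.

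- **4.3, duration of treatment.** Drug runs until the catheter is removed, "until one of the study outcomes is achieved, or until the end of the follow-up".
- **4.3, next sentence.** Medication is to be held in several situations, one of which is that the patient bleeds. No grade of bleeding is given.
- **4.15.** "Study drug is discontinued, and appropriate clinical management is initiated in the case of the following outcome events (as defined in section 4.5"). No list follows. For a participant who reaches an endpoint, "subsequent treatment will be left up to the discretion of the treating physician and documented". Resumption of study drug is not mentioned.
- **4.5.** After the pilot's feasibility measures, the clinical outcomes of the full trial are given: symptomatic VTE as primary, then "Secondary outcomes include major and CRNMB, CVC life span, premature CVC removal, CVC lumen occlusion, CVC associated infection and death".
- **5.3.** A participant with major bleeding (ISTH definition) "will have study drug held until judged safe to resume by the investigator". For the rivaroxaban arm it adds that treatment is stopped temporarily for hemorrhagic complications, and that resumption is considered at the discretion of the treating physicians.

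Section 4.2 states that in the pilot "clinical data will be collected using the same methodology as the proposed full-sized trial", and 4.14 has bleeding assessed at the follow-up contacts.

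**The concern.** A major bleed or CRNMB is both an outcome and a bleeding episode. As an outcome it ends study drug under 4.3 and 4.15. As a bleeding episode it leads to a hold under 4.3 and 5.3, and 5.3 allows a restart. A site cannot follow both, and the protocol ranks neither above the other.

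This is a safety instruction in an anticoagulant trial, so whether a participant is re-exposed after a bleed may depend on which section the site consulted. Three statistical quantities depend on the same choice:

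- drug exposure in the rivaroxaban arm;
- the secondary feasibility measure of good adherence (80% or more of medication taken);
- who counts as not having completed the allocated treatment plan, and so is dropped from the 8.1.4 sensitivity analysis.

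Section 7.2 also names non-compliance with dosing as an example of a protocol violation. With two rules in force, either action could be recorded as one.

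**Working it through.** The protocol states no figure on this point, so the check is mainly a comparison of texts, by type of bleed.

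| Event | Wording that ends drug | Wording that only holds drug |
|---|---|---|
| Major bleeding | 4.3 (outcome reached); 4.15 through 4.5 | 4.3 (bleeding); 5.3 (held, restart possible) |
| CRNMB | 4.3 (outcome reached); 4.15 through 4.5 | 4.3 (bleeding); 5.3 (temporary stop for hemorrhagic complications) |
| Bleeding that is neither | none through 4.5, which does not name it | 4.3 (bleeding); 5.3 (temporary stop for hemorrhagic complications) |

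**Step 1: is the 4.3 outcome wording a final stop?** Its two companions in the same sentence, catheter removal and the end of follow-up, are both ends of treatment. The outcome item reads the same way.

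**Step 2: could 4.15 mean a temporary stop?** Section 5.3 says so expressly when it means a temporary stop. Section 4.15 has no such qualifier and passes later treatment to the treating physician.

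**Step 3: do the 4.5 clinical outcomes apply in the pilot?** The pilot's own outcomes are recruitment, consent, loss to follow-up, adherence and the eligible proportion. None of these is an event that could stop one participant's drug or call for clinical management. The events meant in 4.15 must therefore be clinical ones, and 4.2 and 4.14 collect these in the pilot.

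**Step 4: is there a precedence rule or an exemption for bleeding?** None was found. The two rules stand in adjacent sentences of 4.3, so the conflict exists even within that section.

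**Number of participants.** Inputs: 100 pilot participants (8.2) and 1:1 allocation (4.7), so 100 / 2 = 50 on rivaroxaban. The protocol gives no bleeding rate; 2 to 10% for major bleeding or CRNMB is an assumption.

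- Low: 0.02 × 50 = 1
- High: 0.10 × 50 = 5

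**Effect on adherence, as an illustration.** Assume the denominator is the 90 planned daily doses; 4.5 does not define it. Good adherence then needs 0.80 × 90 = 72 doses, so at most 90 − 72 = 18 may be missed. A participant stopped for good before taking 72 doses is classed as not adherent. A participant who is held and restarted, and misses no more than 18 doses in all, is classed as adherent. The same bleed can thus change the classification according to the section followed. If the denominator were only the doses due before a stop, this effect would shrink or vanish.

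**Effect on the sensitivity analysis.** Section 8.1.4 removes participants who did not complete the allocated plan. Whether a participant stopped after a bleed, or held and restarted, has completed that plan depends on which rule is the plan. Only the rivaroxaban arm takes study drug, so this ambiguity falls on that arm.

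**The case against.** The strongest reply is that the text written for bleeding is consistent. The hold sentence in 4.3 and the dedicated section 5.3 agree, while the opposing wording is generic. A site faced with a major bleed would naturally turn to the section on managing it. That is a reasonable guess at the intent, but the protocol does not state this precedence. The sentence of 5.3 with an explicit restart provision names major bleeding only, so CRNMB is less clearly covered. Section 5.3 also places the decision to resume with the investigator in one sentence and with the treating physicians in another.

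A second reply is that 4.15 announces events without listing them, so its reach is unknown. This stands in part. A reader might infer that every item in 4.5, including lumen occlusion and catheter infection, ends treatment. The text does not settle that: the 4.5 list includes catheter life span, which is not an event, so an all-items reading can hardly be intended. The missing list is itself a defect, and the 4.3 wording produces the conflict without 4.15.

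Three further inferences go beyond the documents.

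- **That sites will differ.** There are three centres, and one coordinator trains and monitors them (6.1). The text shows only that they may differ. Since 5.3 leaves resumption to judgement, some variation would remain even if it were the only rule.
- **That recurrent bleeding, or the main comparison, would be compromised.** No recurrent-event analysis is planned. Section 4.3 has all patients followed for 90 days unless they die or withdraw permission, and 8.1.4 analyses by intention to treat. Neither outcome capture nor arm membership depends on whether drug was held or stopped.
- **That the same share of the full trial's 860 per arm would be affected.** This protocol governs a pilot of 100. Section 4.2 allows for design changes before the full trial, and nothing shows that these sentences would be carried over unchanged.

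**Conclusion.** Wrong as written. For major bleeding and CRNMB, the protocol both ends study drug (4.3, and 4.15 through 4.5) and only holds it (4.3 and 5.3), with nothing to say which applies. This conclusion rests on the wording alone and needs no bleeding rate.

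Its size is limited: about 1 to 5 of 50 rivaroxaban participants in the pilot, if 2 to 10% have such a bleed. It reaches drug exposure, the 80% adherence measure and the supplementary set in 8.1.4. That analysis belongs to the full trial, but 4.2 allows pilot data to enter it. The mean monthly recruitment per site (8.1.2) and the intention-to-treat comparisons are not directly affected. Lesser bleeding is outside the point, because 4.5 does not name it. The reason to act is that an instruction bearing on participant safety cannot be followed as it stands.

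**What to change.** Reconcile 4.3, 4.15 (with 4.5) and 5.3 so that one instruction applies to study drug after a bleeding outcome, with the same wording or a cross-reference in each place. In 4.15, supply the missing list, naming the 4.5 events that trigger discontinuation. In the same amendment, make the two sentences of 5.3 agree on who decides about resumption. Which rule applies, and to which events, is a clinical choice for the sponsor, and no view is taken here.

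The cost is amendment wording only. Sample size, visits and the planned analyses do not change.
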